11.1 Adverse Events

Adverse events will be coded by system organ class and preferred term using the *Medical Dictionary for Regulatory Activities (MedDRA)*, version 21.1 or newer.

An AE will be considered a treatment-emergent adverse event (TEAE) if the AE began or worsened (increased in severity or became serious) on or after the date of the first dose of double-blind study intervention. However, an AE that occurs more than 30 days after the last dose of study intervention will not be counted as a TEAE. Per case report form instructions, a new AE record will be created with a new AE onset date for any AE that worsens. Therefore, TEAEs can simply be identified as those AEs with recorded onset date on or after the date of the first dose of double-blind study intervention and within 30 days of the last dose of double-blind study intervention.

An AE will be considered a treatment-emergent SAE (TESAE) if it is a TEAE that also meets SAE criteria. The number and percent of participants with TEAEs, TEAEs leading to discontinuation, Deaths, and TESAEs will be presented by treatment.

The number and percentage of participants reporting TEAEs in each treatment group will be tabulated by descending percentage in the RLM group, by system organ class (SOC) and preferred term and by system organ class, preferred term, and severity.

The number and percentage of participants reporting treatment related TEAEs will be tabulated by system organ class and preferred term.

If more than 1 AE is coded to the same preferred term for the same participant, the participant will be counted only once for that preferred term using the greatest severity for the summarization by severity.

The number and percentage of participants in the Safety Population who have TEAEs leading to premature discontinuation of the study treatment will be summarized by SOC/ preferred term and treatment.

The incidence of common ($\geq 2\%$ of participants in any treatment group) TEAEs will be summarized by system organ class, preferred term, and treatment group.

The number and percentage of participants who have TESAE will be summarized by SOC/preferred term and treatment group.

In addition, separate tabular displays for participants who died, participants with SAEs, participants with TEAEs leading to premature discontinuation will be presented.

11.1.1 AEs of Special Interest

Hyperglycemia- and hypoglycemia-related events and potential Major Adverse Cardiovascular Events (MACE) listed on the [Table 11.1.1-1](#) below are considered AEs of special interest (AESI).

Table 11.1.1-1. AEs of Special Interest

Category	Adverse Event or Preferred term	
Hyperglycemia	Blood glucose increased Diabetes mellitus inadequate control Diabetes with hyperosmolarity Diabetic coma Diabetic hyperglycaemic coma Diabetic hyperosmolar coma Diabetic ketoacidosis	Diabetic ketoacidotic hyperglycaemic coma Hyperglycaemia Hyperglycaemic seizure Hyperglycaemic unconsciousness Hyperosmolar hyperglycaemic state Ketoacidosis
Hypoglycemia	Blood glucose decreased Hypoglycaemia Hypoglycaemia unawareness Hypoglycaemic coma	Hypoglycaemic encephalopathy Hypoglycaemic seizure Hypoglycaemic unconsciousness Shock hypoglycaemic
MACE	Death from cardiovascular causes Non-fatal myocardial infarction Non-fatal stroke	

An AE will be considered a treatment-emergent AESI (TEAESI) if it is a TEAE that also is an AESI. The number and percentage of participants in the Safety Population who have TEEAESI will be summarized by AESI Category, Adverse Event/Preferred Term and treatment group.

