With respect to laboratory findings, in some participants glycemic control may have been negatively affected by the introduction of relamorelin. There were trends in increasing haemoglobin A1c (HbA1c) values after the initiation of relamorelin, which increased slightly after approximately 8 weeks, and dose-related trends in fasting hyperglycemia. Otherwise, no clinically relevant abnormalities were seen for other laboratory tests, including liver function tests, electrocardiograms (ECGs), physical examination findings, and injection site reactions; anti-drug antibodies (ADAs) were not found.

A detailed description of the chemistry, pharmacology, efficacy, and safety of relamorelin is provided in the investigator's brochure (Relamorelin Investigator's Brochure).

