5.5. Justification for Dose

[figure not shown]
Study RM-131-009 was a 12-week Phase 2b, randomized, double-blind, placebo-controlled, parallel group study to evaluate the safety and efficacy of relamorelin in diabetic participants with moderate to severe DG. The doses included within the study were 10 µg BID, 30 µg BID, and 100 µg BID. In general, all doses tested within RM-131-009 appeared to demonstrate meaningful reductions in overall DG symptom scores including vomiting episodes, with acceptable safety and tolerability. The frequency of vomiting episodes was reduced from baseline over the 12-week Treatment Period to a similar extent for participants who received the 3 doses of relamorelin and placebo. Based upon the observed dose response of change-from-baseline symptom scores collected daily over the course of 12 weeks using the DGSSD, the 30 µg BID, and 100 µg BID doses demonstrated apparent maximal symptom score improvements, while the 10 µg BID dose achieved near maximal improvements. Of note, the twice-a-day regimen of relamorelin appears to be necessary for effective symptom relief; the 10 µg once daily study treatment did not demonstrate significant improvement in symptom relief compared to placebo after 28 days of dosing in Study RM-131-004.

Review of the safety laboratory data collected in RM-131-009 revealed an apparent dose-related increase in HbA1c values. Although the variability in HbA1c response was high across all treatments, the 30 µg BID and 100 µg BID doses demonstrated apparent maximal changes in HbA1c values, while the 10 µg BID dose resulted in an approximately half-maximal increase

██████████
Relamorelin

10. Able to provide written informed consent (IC) prior to any study procedures and willing and able to comply with study procedures (as defined in Appendix 3)

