9.2.7.2. Inadequate Control of Diabetes: Hyperglycemia and Hypoglycemia

The irregular and delayed emptying of the stomach in DG has a major effect on the presentation of ingested carbohydrate to the small intestine for absorption, complicating the dosing of hypoglycemic agents (including insulin) used to manage glycemia. Participants should be closely monitored for changes to their diabetes control while in the study, and events related to hyperglycemia or hypoglycemia that are considered to be clinically significant should be reported as AEs (Section [9.2.1](#)).

Relamorelin

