9.4.4. Clinical Safety Laboratory Assessments

- See [Appendix 2](#) for the list of clinical laboratory tests to be performed and refer to the SoA (Section 2) for the timing and frequency.
- The investigator must review the laboratory report, document this review, and record any clinically relevant changes occurring during the study in the AE section of the eCRF. The laboratory reports must be filed with the source documents. Clinically significant abnormal laboratory findings are those that are not associated with the underlying disease, unless judged by the investigator to be more severe than expected for the participant's condition.
- All laboratory tests with values considered clinically significantly abnormal during participation in the study or within 30 days after the last dose of study treatment should be repeated until the values return to normal or baseline or are no longer considered clinically significant by the investigator or MSP.
 - If such values do not return to normal/baseline within a period of time judged reasonable by the investigator, the etiology should be identified and the sponsor notified.
 - All protocol-required laboratory assessments, as defined in [Appendix 2](#), must be conducted in accordance with the laboratory manual and the SoA.
 - If laboratory values from non-protocol specified laboratory assessments performed at the institution's local laboratory require a change in participant management or are considered clinically significant by the investigator (eg, SAE or AE or dose modification), then the results must be recorded in the eCRF.

Relamorelin

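### The closed term list for the hyperglycaemia AESI (SAP Table 11.1.1-1) has no raised-HbA1c term, so an AE coded only that way is left out of the AESI summary

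*SAP*

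**What the plan says.** SAP Section 11.1.1 states that the events in Table 11.1.1-1 "below are considered AEs of special interest (AESI"), and that a treatment-emergent AESI is a treatment-emergent AE (TEAE) that is also one of these. The list is therefore closed. Its Hyperglycemia row begins "Blood glucose increased Diabetes mellitus inadequate control Diabetes with hyperosmolarity". The planned output is the number and percentage of participants by category, term and treatment group.

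Protocol Section 3.2 reports from Phase 2b "trends in increasing haemoglobin A1c (HbA1c) values after the initiation of relamorelin" and "dose-related trends in fasting hyperglycemia". It also reports more hyperglycaemia-related AEs than on placebo, and three ketoacidosis events. Protocol Section 5.5 says the safety laboratory data "revealed an apparent dose-related increase in HbA1c values", with roughly half the maximal increase at 10 µg BID, the dose used in this trial.

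Two protocol sections govern what reaches the AE page. Section 9.2.7.2, on inadequate control of diabetes, says that "events related to hyperglycemia or hypoglycemia that are considered to be clinically significant should be reported as AEs". Section 9.4.4, on laboratory tests in general, says: "Clinically significant abnormal laboratory findings are those that are not associated with the underlying disease, unless judged by the investigator to be more severe". Severity there is judged against what that participant's disease would lead one to expect.

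Outside the AESI table, HbA1c is a named secondary safety endpoint (Protocol Section 4). SAP Sections 11.2 and 11.5 analyse it with the laboratory data. Table 11.2-1 sets potentially clinically significant (PCS) criteria at increases of at least 0.5% and at least 1%.

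**The concern.** The protocol treats worsening glycaemic control as a potential risk of the drug, and the AESI summary is where a reader would look for the grouped AE count on it. HbA1c is a standard measure of that control and one of the signals seen before. Leaving out its term follows no visible principle, because the row already admits *Blood glucose increased*, which is also only a laboratory result.

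The consequence is that counting depends on words. Suppose two participants have the same HbA1c rise. One is reported as *Diabetes mellitus inadequate control* and counts; the other is reported as raised HbA1c and does not. At stake is the completeness of one safety grouping, not the detection of HbA1c change as such.

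**Working it through.** No figure in the plan bears on this, so there is none to reproduce. The check sets the texts side by side.

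**Step 1: the 13 terms by kind.** Glucose level or hyperglycaemia, 2; inadequate control, 1; coma, 4; hyperosmolar states, 2; ketoacidosis, 2; seizure or unconsciousness, 2. Sum: 2 + 1 + 4 + 2 + 2 + 2 = 13. Terms naming HbA1c or glycated haemoglobin: 0.

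**Step 2: reported signals against the list.**

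| Signal in the protocol | Section | Listed term available? |
|---|---|---|
| Hyperglycaemia-related AEs | 3.2 | Yes |
| Diabetic ketoacidosis | 3.2 | Yes |
| Fasting hyperglycaemia | 3.2 | Yes, if reported as an AE |
| HbA1c rise | 3.2, 5.5 | No dedicated term |

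Three of the four are covered.

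**Step 3: follow an AE coded only as raised HbA1c.**
- TEAE tables by system organ class and preferred term (SAP 11.1): counted.
- AESI summary (SAP 11.1.1): not counted.
- Laboratory summaries (SAP 11.2): the measured value enters whether or not an AE was reported.

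A reader cannot repair the AESI count by adding the raised-HbA1c line from the TEAE table, because some participants may have both that event and a listed one.

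**Step 4: what an undercount would do.** Let p be the true proportion with a reported glycaemic-worsening AE in an arm, and m the share of those participants whose only such AE is coded as raised HbA1c. The table shows p(1 − m). If m is the same in both arms, then

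difference shown = (p_R − p_P)(1 − m), and ratio shown = p_R / p_P, unchanged.

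Neither p nor m is in the documents. Purely as an assumption, take 10% and 5% of 300 per arm:

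| m | Relamorelin | Placebo | Difference (points) | Ratio |
|---|---|---|---|---|
| 0 | 10% | 5% | 5.0 | 2.0 |
| 10% | 9% | 4.5% | 4.5 | 2.0 |
| 25% | 7.5% | 3.75% | 3.75 | 2.0 |
| 50% | 5% | 2.5% | 2.5 | 2.0 |

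This shows the mechanism only. It does not estimate the loss, which may be nil.

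**The case against.** The strongest reply is that HbA1c is handled by a better route. Protocol Section 10.3.3 lists glycaemic events under AEs and HbA1c as a separate study-specific assessment. The SAP then gives change from baseline by arm, shift tables, PCS counts at two thresholds, and a display of all AEs in participants with PCS laboratory values. These outputs use measured values and do not depend on AE wording. That stands, and it limits the gap to one table. They are not a full substitute, however. A participant already high at baseline cannot worsen in a low/normal/high shift table. The PCS percentage also requires a non-PCS baseline, which has no meaning when the criterion is itself a change from baseline.

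A second reply is that investigators can use *Diabetes mellitus inadequate control*, which is listed and was reported as a serious AE in Phase 2b. That also stands, but nothing requires them to prefer it.

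Three stronger readings are tempting and are not supported:

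- **That the list misses the form of worsening seen in Phase 2b.** It misses one of four reported signals.
- **That Section 9.4.4 tells sites not to record glycaemic laboratory changes because diabetes is the underlying disease.** The same section requires clinically relevant changes to be entered as AEs and keeps findings more severe than expected, while Section 9.2.7.2 specifically asks for clinically significant glycaemic events. What remains is that neither section sets a threshold or says which governs.
- **That the comparison is shown to be biased toward no difference.** With equal proportional loss the absolute difference shrinks but the ratio does not, and the documents give no ground for assuming unequal loss. The AESI summary is descriptive, so no test loses power.

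**Conclusion.** The point holds as a narrow omission: the AESI list has a term for raised glucose and none for raised HbA1c, although a dose-related HbA1c rise is among the protocol's own signals. The AESI summary can therefore undercount glycaemic worsening, by an amount the documents do not allow anyone to calculate. It would be wrong to infer that HbA1c worsening escapes the safety analysis, since it remains in the laboratory outputs and any reported AE remains in the TEAE tables.

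This rests on two assumptions: that some investigators report the finding as raised HbA1c, and that it is then coded to a term other than the 13 listed. If either fails, nothing is lost.

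The practical weight is small. The trial was terminated on 04 September 2020, and the SAP says the full planned analyses no longer apply. Whether the abbreviated report keeps the AESI table depends on SAP Section 19.2, and the protocol's AESI definitions are in Appendix 4; neither is in the text available here.

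**What to change.** Add the preferred term or terms that the MedDRA version in use assigns to raised HbA1c to the Hyperglycemia row of SAP Table 11.1.1-1, wherever that table is produced. This is one line of SAP text and needs no new data. The downside is slightly higher AESI counts in both arms.

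Optionally, show the existing counts of HbA1c increases of at least 0.5% and at least 1% beside the AESI table as a separate row with its denominator stated. They should not be merged into the AESI count, because mixing investigator-reported events with laboratory thresholds would change what an AESI means.

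A change to the reporting rules would come too late for this terminated trial. Any protocol that reuses the text should reconcile Sections 9.4.4 and 9.2.7.2 by stating which governs the reporting of glucose and HbA1c findings. None of this touches glycaemic management.

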11.1.2 Medical Device Incidents (Including Malfunctions)

The number and percentage of participants in the Safety Population who have AEs related to study device (ie., pen injector) will be summarized by preferred term and treatment. In addition, the number and percentage of participants in the Safety Population with device malfunctions will be summarized by treatment.

Medical device incidents and device malfunctions during run-in period will be only presented in the Listing.

11.2 Clinical Laboratory Parameters

Descriptive statistics for clinical laboratory values (in SI units) and changes from the baseline values at each assessment time point will be presented by treatment group for the following laboratory parameters:

Hematology	Platelet count	RBC count	Hemoglobin	Hematocrit
	% Reticulocytes	WBC count	Neutrophils	Lymphocytes
	Monocytes	Eosinophils	Basophils	
Clinical Chemistry	BUN	Creatinine	Fasting blood glucose	Hemoglobin A1c
	Potassium	Chloride	Bicarbonate	Sodium
	Calcium	Phosphorus	Uric acid	Aspartate
	aminotransferase	Alanine aminotransferase		Alkaline
	phosphatase	Total bilirubin	Direct bilirubin	Total protein
	Albumin	cholesterol	triglycerides	HDL
	cholesterol	LDL cholesterol		
Other Laboratory Assessments	C-peptide			
Urinalysis	pH	Specific gravity		

Clinical laboratory test values will be considered potentially clinically significant (PCS) if they meet either the lower-limit or higher-limit PCS criteria listed in [Table 11.2-1](#). The number and percentage of participants who have PCS postbaseline clinical laboratory values will be tabulated by treatment group for the double-blind Treatment Period. The percentages will be calculated relative to the number of participants with available non-PCS baseline values and at least 1 postbaseline assessment for the double-blind treatment period. The numerator will be the total number of participants with available non-PCS baseline values and at least 1 PCS postbaseline value for the double-blind Treatment Period. A supportive tabular display of participants with PCS postbaseline values will be provided, including the PID number, trial center number, and baseline and all postbaseline (including non-PCS) values.

In addition, tabular displays showing all AEs that occurred in participants who had PCS postbaseline clinical laboratory values will be provided.

Shift tables from baseline to end of trial (EOT) for clinical laboratory parameters will be presented by treatment group for the following categories: low, normal, and high.

Table 11.2-1. Criteria for Potentially Clinically Significant Laboratory Tests

Parameter	SI Unit	Lower Limit	Higher Limit
CHEMISTRY			
Albumin	g/L	< 0.9 * LLN	> 1.1 * ULN
Alanine Aminotransferase (ALT)	U/L	—	≥ 3 * ULN
Alkaline Phosphatase	U/L	—	≥ 3 * ULN
Aspartate Aminotransferase (AST)	U/L	—	≥ 3 * ULN
Calcium	mmol/L	< 0.9 * LLN	> 1.1 * ULN
Chloride	mmol/L	< 0.9 * LLN	> 1.1 * ULN
Cholesterol	mmol/L	—	> 1.6 * ULN
Creatinine	µmol/L	—	> 1.3 * ULN
Potassium	mmol/L	< 0.9 * LLN	> 2.0 * ULN
Glucose, Fasting	mmol/L	< 0.9 * LLN	> 2.5 * ULN
Glycohemoglobin A1C	%		Increase of ≥ 0.5%
Glycohemoglobin A1C	%		Increase of ≥ 1%
Sodium	mmol/L	< 0.9 * LLN	> 1.1 * ULN
Total Bilirubin	µmol/L	—	> 1.5 * ULN
Total Protein	g/L	< 0.9 * LLN	> 1.1 * ULN
Triglycerides, Fasting	mmol/L	—	≥ 3 * ULN
Urea (BUN)	mmol/L	—	> 1.2 * ULN
Magnesium	mmol/L	< 0.9 * LLN	> 1.1 * ULN
Bicarbonate	mmol/L	< 0.9 * LLN	> 1.1 * ULN
Phosphate	mmol/L	< 0.9 * LLN	> 1.1 * ULN
Uric Acid	µmol/L	< 0.9 * LLN	> 1.1 * ULN
HEMATOLOGY			
Basophils Absolute Cell Count	10 ⁹ /L	—	> 3 * ULN
Eosinophils Absolute Cell Count	10 ⁹ /L	—	> 3 * ULN
Hematocrit	Ratio	< 0.9 * LLN	> 1.1 * ULN
Hemoglobin	g/L	< 0.9 * LLN	> 1.1 * ULN
Lymphocytes Absolute Cell Count	10 ⁹ /L	< 0.8 * LLN	> 1.5 * ULN
MCH	PG	—	> 3 * ULN
MCHC	G/L	—	> 3 * ULN
MCV	fL	< 0.9 * LLN	> 1.1 * ULN
Monocytes Absolute Cell Count	10 ⁹ /L	—	> 3 * ULN
Neutrophils Absolute Cell Count	10 ⁹ /L	< 0.8 * LLN	> 1.5 * ULN
Platelet Count	10 ⁹ /L	< 0.5 * LLN	> 1.5 * ULN

Table 11.2-1. Criteria for Potentially Clinically Significant Laboratory Tests

Parameter	SI Unit	Lower Limit	Higher Limit
Red Blood Cell Count (Erythrocyte Count)	$10^{12}/L$	< 0.9 * LLN	> 1.1 * ULN
White Blood Cell Count	$10^9/L$	< 0.7 * LLN	> 1.5 * ULN
URINALYSIS			
pH		< 0.9 * LLN	> 1.1 * ULN
Specific Gravity		—	> 1.1 * ULN

LLN: Lower limit of normal value provided by the laboratory.

ULN: Upper limit of normal value provided by the laboratory.

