Gastroparesis (GP) is a disorder characterized by delayed GE, such that movement of food from the stomach to the small intestine is delayed. The pathophysiology of GP has not been fully elucidated but seems to involve abnormalities in the autonomic nervous system (vagus nerve), smooth muscle cells, enteric neurons, and interstitial cells of Cajal; in DG, change in the type of macrophages in the gastric musculature suggest a role for inflammation as a cause of delayed GE.

Diabetes mellitus, either type 1 or 2 (T1DM/T2DM), is considered to be the most common, specifically identifiable cause of GP. This complication is a result of chronically elevated blood glucose levels, which are known to damage nerve structure in general, and the vagus nerve in particular, and negatively affect function ([Parkman 2004](#)).

DG is a chronic condition that requires prolonged treatment. Core signs and symptoms of DG are nausea, abdominal pain, post-prandial fullness, bloating, vomiting, and early satiety (a feeling of fullness after eating just a few bites) ([Camilleri 2013](#)). These symptoms can be debilitating and, when uncontrolled, have a significant negative impact on patient quality of life and functioning, including work productivity ([Camilleri 2011](#), [Parkman 2011](#)). Serious adverse sequelae of DG include: potentially life-threatening dehydration due to persistent vomiting, gastroesophageal reflux disease (GERD) that can advance to esophagitis, formation of bezoars, difficulty managing blood glucose levels, and malnutrition due to poor absorption of nutrients or a low-calorie intake ([U.S. Department of Health and Human Services, 2012](#)). Aside from the impact on patients, these events often lead to hospitalization ([Koch 2016](#)), resulting in a high economic burden for health care systems.

Relamorelin

DG complicates management of blood glucose for both T1DM and T2DM patients due to carbohydrates being delivered to and therefore absorbed from the small intestine at unpredictable times (Rayner 2001). As a result, diabetic patients with DG often have poorly controlled diabetes, frequently with alternating hypo- and hyperglycaemia, especially if treated with insulin.

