16.10 Character Values of Clinical Laboratory Parameters

If the reported value of a clinical laboratory parameter cannot be used in a statistical summary table because, for example, the value is a character string rather than a numerical type, a coded value needs to be appropriately determined and used in the statistical analyses. However, the actual values as reported in the database will be presented in data listings.

Table 16.10-1. Examples for Coding of Special Character Values for Clinical Laboratory Parameters

Laboratory Test (Unit)	Possible Lab Results (in SI units)	Coded Value for Analysis
Chemistry: ALT	< 5	0
Chemistry: AST	< 5	0
Chemistry: Bilirubin, Total	< 2	0
Urinalysis: Glucose	= OR > 55, >= 55, > 0	Positive
	<= 0, Negative	Negative
Urinalysis: Ketones	= OR > 8.0, >= 8.0, > 0	Positive
	<= 0, Negative	Negative
Urinalysis: pH	> 8.0, >= 8.0	8.0
	>= 8.5,	8.5
Urinalysis: Protein	= OR > 3.0, >= 3.0, > 0	Positive
	<= 0	Negative

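### The only PCS limit for urine specific gravity (above 1.1 x ULN) is effectively unreachable, so that row of the safety table is empty by construction

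*SAP*

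**What the plan says.** SAP Section 11.2 lists specific gravity and pH as the two urinalysis parameters to be summarised. A laboratory value counts as PCS "if they meet either the lower-limit or higher-limit PCS criteria listed in" Table 11.2-1.

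- **Specific gravity** has a dash in the lower-limit column and one upper criterion: "Specific Gravity — > 1.1 * ULN".
- **Urine pH** has limits on both sides: "pH < 0.9 * LLN > 1.1 * ULN".
- **Reference limits** come from the laboratory. The table note says "ULN: Upper limit of normal value provided by the laboratory", and no numerical range is printed for either parameter.

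Three outputs in Section 11.2 depend on the flag. The first is the tabulation: "The number and percentage of participants who have PCS postbaseline clinical laboratory values will be tabulated by treatment group". The second is a supportive display of the flagged participants' values, and the third a display of all AEs in those participants. The denominator is participants with a non-PCS baseline and at least one postbaseline assessment. Section 16.4 adds that every postbaseline assessment is used in deciding PCS status.

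**The concern.** A limit of 1.1 times ULN reads as a modest margin of 10% above normal. That reading suits a quantity whose scale starts at zero, such as sodium or hematocrit, which carry the same multiplier in this table. Specific gravity does not start at zero: plain water is already 1.000, and the clinical information lies in the small excess above that. Multiplying the whole number by 1.1 adds at least 0.100 to a limit whose own excess over water is only a few hundredths.

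At stake is one row of a safety table, and whether its zeros mean anything. The protocol's Introduction (Section 3) lists "potentially life-threatening dehydration due to persistent vomiting" among the serious consequences of the disease. Specific gravity is the one of the two urinalysis parameters that reflects urine concentration. A row with no flagged participants in either arm would look like a finding about concentrated urine when it is only a consequence of the threshold.

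**Working it through.** **Inputs**

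- Multiplier 1.1, upper side only: SAP Table 11.2-1.
- ULN: supplied by the laboratory and not given in the documents. Assumed range 1.020 to 1.040.
- Water at 1.000: the definition of the scale, not a figure in the documents.
- Highest specific gravity that urine can reach: not given in the documents. Assumed to be below 1.100.

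The SAP states no figure for this limit, so there is none to reproduce.

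**Step 1. The limit**

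Limit = 1.1 x ULN. The floor, at ULN = 1.000 (water itself), is 1.1 x 1.000 = 1.100. Excess over water is the value minus 1.000.

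| Assumed ULN | Limit | Excess at ULN | Excess at limit | Ratio |
|---|---|---|---|---|
| 1.020 | 1.122 | 0.020 | 0.122 | 6.1 |
| 1.030 | 1.133 | 0.030 | 0.133 | 4.4 |
| 1.040 | 1.144 | 0.040 | 0.144 | 3.6 |

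On the part of the scale that carries information, the rule therefore asks for about 4 to 6 times the excess that the laboratory already calls the upper limit of normal.

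**Step 2. The same check in reverse**

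A result x is flagged only if ULN < x / 1.1. For x = 1.040, ULN would have to be below 1.040 / 1.1 = 0.945, which is below water. For x = 1.100, ULN would have to be below 1.100 / 1.1 = 1.000. So no result up to 1.100 can be flagged for any ULN of 1.000 or more. The conclusion does not depend on which laboratory range applies.

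**Step 3. What follows for the outputs**

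Specific gravity has no lower criterion, so nothing else can produce a flag. The numerator is zero in each arm whatever the sample size, and the two linked displays have no entries for this parameter.

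**Step 4. What the remaining outputs cover**

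Section 11.2 also provides descriptive statistics with changes from baseline at each time point, and low/normal/high shift tables. The shift tables run from baseline to end of trial. PCS status uses all postbaseline assessments (Section 16.4). A high value mid-study that has resolved by the end of trial therefore falls outside the shift table, and the PCS rule cannot catch it either. Summary statistics, which include the maximum (Section 11.0), could show that such a value occurred, but they give no participant count and no link to AEs.

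**The case against.** The strongest case on the other side is that little is lost.

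- **Shift tables.** A move from normal to high specific gravity at end of trial will be shown. This stands, apart from the transient elevations described above.
- **Other signals of dehydration.** Table 11.2-1 has upper limits for BUN (above 1.2 x ULN), creatinine (above 1.3 x ULN), sodium, hematocrit and albumin. Table 11.3-1 flags low blood pressure, high pulse rate and weight loss of at least 7%, and AEs are tabulated separately. This also stands: the plan is not blind to dehydration, and it is not certain that anyone would read the empty row as reassurance.
- **Termination.** SAP Section 4.0 says that the full analyses no longer apply and that only an abbreviated report will be written. It refers to Section 19.2 (Appendix 2) for the retained analyses, which is not in the supplied text. This limits how much the point matters in practice, but the criterion remains in the current SAP.

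Two stronger readings are tempting, and the documents do not support them.

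- **A reader might infer that the urine pH count is also zero by construction**, because SAP Table 16.10-1 shows 8.5 as its highest coded pH and 1.1 x ULN exceeds 8.5 once ULN is above 8.5 / 1.1 = 7.73. But pH also has a lower limit, and either limit is enough. At an assumed LLN of 5.5 the lower limit is 0.9 x 5.5 = 4.95, so a pH of 4.5 is flagged. Table 16.10-1 gives examples for results that cannot be summarised as reported, and it does not cap numeric results. At an assumed ULN of 8.0 the upper limit is 8.8, and a numeric 9.0 exceeds it.
- **A reader might state the specific gravity result as 0 of 600.** That is the planned enrolment of a study that stopped early. The denominator in Section 11.2 is participants with a non-PCS baseline and a postbaseline assessment, and that number is not known here.

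**Conclusion.** The point holds for urine specific gravity only. As written, the PCS criterion cannot in practice flag anyone, so the count and the two linked displays carry no information for this parameter in either arm. The limit is at least 1.100 for any ULN of 1.000 or more, and 1.122 to 1.144 for assumed ULNs of 1.020 to 1.040.

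The conclusion rests on one assumption that the documents neither confirm nor contradict: that urine specific gravity does not reach 1.100. It does not depend on the exact ULN.

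The consequence is small. No hypothesis test or efficacy result is affected, and the only coverage lost is of elevations that resolve before the end of trial. The SAP serves both RLM-MD-01 and RLM-MD-02, so the same cell applies to both. Whether the table is still produced after termination cannot be determined from the supplied text.

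**What to change.** Change one cell in SAP Table 11.2-1. Replace the specific gravity criterion with a limit on the reportable scale: a value above the laboratory ULN. The existing Section 11.2 rule, which counts only participants with a non-PCS baseline, then restricts the row to participants whose baseline was at or below ULN, so no new denominator is needed.

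If the sponsor prefers not to define a new limit, either remove specific gravity from the PCS table or add a footnote saying that the limit is effectively unreachable and that zero counts are not informative.

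One check when programming: Table 16.10-1 has no example for specific gravity. If the laboratory reports extreme results as character strings, their coding should be settled before the new limit is applied. A result coded to its own bound would not exceed a ULN equal to that bound.

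The cost is a minor SAP edit. The downside of the new limit is some trivial flags and overlap with the high category of the shift table, because the margin between abnormal and PCS disappears for this parameter. The urine pH row needs no change on these grounds.
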